2.7 Sample Size Determination

The primary efficacy endpoint is change from Baseline in AISRS total score at Visit 7 (Week 5). A Bonferroni adjustment will be utilized for the primary efficacy analysis where each AR19 dose will be tested against placebo separately using an alpha of 0.025 for each test.

Eighty-seven (87) subjects per treatment group will provide approximately 90% power to detect a 7.0-point difference in mean change from Baseline to Visit 7 in the AISRS total score between one of the AR19 doses and placebo with a standard deviation of 13.0 and Type I error of 0.025 using a two-sample test. To account for an approximate 20% dropout rate, a total of 104 subjects will be randomized to each of the three treatment groups for a total of 312 randomized subjects.

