3. GENERAL ANALYSIS, REPORTING, AND PROGRAMMING CONVENTIONS

This section discusses general policies to be employed in the analysis and reporting of the data from the study. Departures from these general policies may be given in the specific detailed sections of this SAP. When this situation occurs, the rules set forth in the specific section take precedence over the general policies.

Descriptive statistics for continuous parameters will include number of observations (n), mean, median, standard deviation, minimum, and maximum values. Descriptive statistics for categorical parameters will include frequency counts and percentages. All study data will be listed by subject, treatment group, sequence (as applicable), and time point (as applicable).

Hypothesis testing, unless otherwise indicated, will be two-sided and performed at the 2.5% significance level. When confidence intervals are presented, they will be two-sided with a confidence coefficient of 97.5%. P-values will be reported to 3 decimal places if greater than 0.001. If less than 0.001, report '<0.001'. P-values and significant levels will be reported as 0.025 rather than .025.

Data will be summarized based on the recorded visit; no visit windowing will be performed.

No preliminary rounding will be performed; rounding will only occur after analysis. To round, the digit to right of last significant digit will be considered: if < 5 then round down, if ≥ 5 then round up. Means and medians will be presented with one more decimal place than the precision of the data. Standard deviations will be presented with two more decimal places than the precision of the data. Percentages will be presented with one decimal place. Minimums and maximums will be presented with the same precision as the original data.

All analyses will be performed using the SAS System® version 9.3 or higher.

The following general programming conventions will apply:

Exposure Days: (Last dosing date – first dosing date + 1)

Compliance: [(Number of doses taken)/(number of doses planned)]*100

Duration days: (End/resolution date – start/onset date +1)

Study day: (Date of interest – first dosing date +1) if date of interest is on or after the first dosing date: (Date of interest – first dosing date) if date of interest is before the first dosing date.

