7.1.1.2 Missing AISRS Total Scores at Individual Study Visits

Primary Analysis

No imputation of missing AISRS total scores at individual visits will be done for the primary efficacy analysis. The mixed model repeated measures methods used to analyze the primary endpoint has been designed to utilize all available data and provides valid estimates under the assumption of data which are missing completely at random or missing at random. Accordingly, all subjects with one dose of study medication and at least one post-baseline on-treatment assessment of the primary efficacy variable will be included in the model.

Sensitivity Analyses

To explore the sensitivity of the primary analysis results, analyses using two imputation methods may be performed: a placebo-based multiple imputation (MI) pattern-mixture model (PMM) analysis and a tipping point analysis using the PMM. If the dropout rate in this study is <2%, these sensitivity analyses will not be performed. This decision will be made prior to database unblinding.

Sensitivity analysis one: Placebo-based MI PMM

To explore the robustness of the primary analysis results, a sensitivity analysis will be carried out that assesses the situation where the data are not missing at random (NMAR). More specifically, all subjects taking AR19 who discontinue for any reason will be assumed to behave like placebo subjects.

A controlled, multiple imputation approach based on PMM will be applied for those subjects on AR19 using the 'Copy Reference' approach [3]. More specifically, missing data for those subjects taking AR19 who discontinued early will be imputed based on the posterior distribution of the placebo group. Missing data for placebo subjects who discontinue early will also be imputed using the observed

values of the placebo group.

Data will be imputed using SAS PROC MI (v9.3 or later) using the full conditional specification method (FCS). Twenty burn-in iterations will be performed prior to each imputation. The imputation model will include observed non-missing AISRS scores, baseline AISRS score, age, and sex. One hundred imputed datasets will be generated for analysis.

The same model used in the primary analyses will be fit to each of the 100 datasets. The parameter estimates and standard errors will be combined using PROC MIANALYZE in SAS v 9.3 or higher.

Sensitivity analysis two: Tipping Point Analysis using PMM

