The goal of the tipping point analysis is to determine how robust the results of the primary analysis are to varying its assumption that the change from baseline at Visit 7 AISRS total scores for subjects that discontinue early from the AR19 group is the same as the completers in the AR19 group. In particular, this analysis examines how altering this assumption to allow the discontinued subjects to have better and worse outcomes will impact the resulting estimates of the treatment effect. This will quantify the range of values which the assumptions can take on and still provide the same conclusions as the primary analysis, giving a very direct measure of the sensitivity of the primary analysis to deviations from the assumptions using an approach that has missing values for AR19 discontinuation subjects imputed. Missing AISRS total score data in the AR19 group will be imputed based on observed values in the AR19 group and likewise, missing AISRS total score values in the placebo group will be imputed based on observed values in the placebo group.

In this analysis, the estimate of the effect in the AR19 subjects may be viewed as a weighted average of the observed average for AR19 completers and the average MAR estimate for AR19 subjects. Shift values of .05 (treated subjects have 5% of the change from baseline AISRS total score as assumed in the primary methodology) through 1 (treated subjects have 100% of the change from baseline AISRS total score as assumed via the primary methodology) will be applied at increments of .05 and reported. The primary analysis will be rerun for all shift values and the resulting treatment difference, 97.5% CI and p-value for each shift value will be reported; the wider the range of values that result in no change in interpretation, the more robust the analysis results may be considered to be.

Subjects receiving placebo who discontinue prior to the end of the treatment period will have their change from baseline AISRS total score value imputed

based on the assumption that they respond to treatment in a similar manner to the placebo subjects who completed the study. For subjects receiving AR19 who discontinue prior to the end of the treatment period, the assumed response to treatment will be examined in increments from worst (subjects respond in a similar manner to the placebo subjects who completed the study) to best (subjects respond in a similar manner to the AR19 subjects who completed the study).

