The steps to implement the tipping point analysis are as follows:

- 1) A mixed model repeated measures (MMRM) model will be run using all observed data and the LS mean in the AR19 group (20 and 40 mg/day separately) of change from baseline at Week 7 in AISRS total score will be calculated.
- 2) Missing data will be imputed based on the MAR assumption using multiple imputation procedure (PROC MI) to create 100 complete datasets with 20 burn-in iterations.
- 3) For subjects in the AR19 dose groups, the imputed values from Step 2 will be “penalized” by adding a percentage (i.e. 5%, 10%, 15%, 20%, etc. of the LS mean treatment difference) of the absolute value of the mean change calculated from Step 1; for the placebo group, no “penalty” will be taken for the imputed values.
- 4) Each newly generated complete dataset from Step 3 will be analyzed using the primary analysis MMRM model and results from all 100 datasets will be combined (PROC MIANALYZE) to generate inferences.
- 5) This analysis (Steps 3-4) will be repeated for a range of values (i.e. 5%, 10%, 15%, 20%, etc. of the treatment difference) until either the tipping point (where statistical significance of the treatment effect is lost) is identified or the 100% penalty is applied.

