7.4 Analysis Methods

7.4.1 Primary Efficacy Analyses – AISRS Total Scores

The primary efficacy analysis will be performed on the FAS population. The primary efficacy outcome is the change from baseline in AISRS total score at Visit 7 (Week 5) in AR19 (20 and 40 mg/day) versus placebo. To account for these comparisons, a Bonferroni multiple comparison adjustment will be utilized. Both comparisons will be conducted at the 0.025 (0.05/2) alpha level. No other adjustments for multiplicity will be applied to any other endpoints or comparisons. Change from Baseline in AISRS at Visit 7 will be compared between each of the two different AR19 dose groups and the placebo group.

The key elements of the primary efficacy analysis are as follows:

Data: AISRS total scores measured at Baseline through Visit 7. All available data will be used; there will be no imputation of missing data.

Model: Restricted maximum likelihood (REML)-based MMRM analysis

Fixed effects: The following fixed effects are planned:

- Treatment (class effect: AR19 20 mg/day, AR19 40 mg/day, placebo)
- Week (class effect: Weeks 1, 2, 3, 4, 5)
- Baseline AISRS total score
- Treatment-by-week interaction

Residual Variance-Covariance Matrix: An unstructured correlation matrix will be used to model the within-patient errors and restricted maximum likelihood estimation will be used. The Kenward-Roger method will be used for the denominator degrees of freedom. Should the model fail to converge with an unstructured covariance matrix, alternative covariance structures will be applied, in the following order, until the model converges: heterogeneous Toeplitz, heterogeneous compound symmetry, then heterogeneous autoregressive(1).

The null hypothesis:

H_0 : Change from baseline AISRS total scores at Visit 7 are the same for AR19 and placebo

will be tested against the two-sided alternative hypothesis

H_1 : Change from baseline AISRS totals scores at Visit 7 are not the same for AR19 and placebo.

Within this model, pairwise comparisons (using least squares [LS] mean contrasts) will be made to compare AISRS at Visit 7 for each AR19 dose level with placebo separately (primary efficacy outcome). Treatments will also be compared at other weeks as secondary analyses. If differences between baseline characteristics exist between the three treatment groups in this comparison, it will be investigated whether adjustment for these characteristics is clinically relevant and necessary as a sensitivity analysis.

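### The tipping-point penalty is defined on conflicting scales, and on the treatment-difference scale it stops near a placebo-like response, usually short of the tipping point at the planned effect and dropout

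*SAP*

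**What the plan says.** The tipping-point analysis is the second of two sensitivity analyses in SAP section 7.1.1.2. Missing AISRS totals are imputed within arm under missing at random (MAR). The imputed AR19 values are then made worse in 5% steps, and the primary model is refitted at each step. Step 5 repeats this "until either the tipping point (where statistical significance of the treatment effect is lost) is identified or the 100% penalty is applied".

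The section gives the size of the penalty in three ways:

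- **Step 5** takes it as a percentage of the treatment difference. This fits the introductory text, which sets the low end for AR19 dropouts at "worst (subjects respond in a similar manner to the placebo subjects who completed the study").
- **Step 3** names the LS mean treatment difference in its parenthesis, but applies the percentage to the absolute mean change from Step 1. Step 1 computes only the AR19 LS mean change.
- **The shift values** in the introductory text run from .05 to 1 and stand for the share of the change from baseline that treated subjects keep.

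Sensitivity analysis one is a Copy Reference multiple imputation in which "all subjects taking AR19 who discontinue for any reason will be assumed to behave like placebo subjects".

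**The concern.** A tipping-point analysis should say how poor the unseen outcomes must be before the conclusion changes. The SAP states that aim: it wants the range of assumptions under which the primary conclusion stands. If the steps end while the result is still significant, the report can say only that the tipping point lies somewhere beyond.

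The region beyond placebo is relevant here. Protocol sections 4.3, 5.3 and 5.6 withdraw subjects who cannot tolerate their dose, so treatment-related dropout on AR19 is built into the design. Sensitivity analysis one already looks at placebo-like outcomes. The tipping-point analysis is the only planned one that could look further.

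The scale matters as much as the stopping rule. The same 100% can mean a placebo-like response or a return to baseline, so two programmers could follow the text and report different robustness results.

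**Working it through.** **Inputs from the documents.** SAP 2.7 plans for "approximately 90% power to detect a 7.0-point difference in mean change from Baseline to Visit 7 in the AISRS" total score, "with a standard deviation of 13.0 and Type I error of 0.025 using a two-sample test", with 87 per arm, about 20% dropout and 104 randomized per arm. On alpha, SAP 7.4.1 says "Both comparisons will be conducted at the 0.025 (0.05/2) alpha level", and SAP 3 says tests "will be two-sided and performed at the 2.5% significance level". The critical value is z = 2.241.

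**The plan's own figure.** The SAP says "Eighty-seven (87) subjects per treatment group will provide approximately 90% power". A noncentral t calculation at n = 87 gives 0.900, so this reproduces. Twenty percent dropout from 104 leaves about 83, so both 87 and 83 are used below.

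- SE at 87 = 13 × √(2/87) = 1.971
- SE at 83 = 13 × √(2/83) = 2.018

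**Treatment-difference scale.** With observed difference D, dropout share d and penalty k as a multiple of D, the estimate is D(1 − kd). It tips at k* = (1 − 2.241 × SE/D)/d. No tip is found by k = 1 if D exceeds 2.241 × SE/(1 − d).

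For D = 7 and d = 0.2:

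| | SE 1.971 | SE 2.018 |
|---|---|---|
| Estimate at 100% | 7 × 0.8 = 5.6 | 5.6 |
| z at 100% | 2.84 (p = 0.0045) | 2.78 (p = 0.0055) |
| Smallest significant D | 4.42 | 4.52 |
| D above which no tip is found | 5.52 | 5.65 |
| k* | 1.84 | 1.77 |
| Tipping penalty, points | 12.9 | 12.4 |

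With SE 1.971, k* is 3.69 at 10% dropout and 1.23 at 30%.

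**How often no tip is found.** For true effect δ this is P(D > 2.241 × SE/(1 − d)) divided by P(D > 2.241 × SE), with D normal about δ. At δ = 7, d = 0.2:

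- SE 1.971: 0.773/0.905, about 0.86
- SE 2.018: 0.748/0.890 = 0.84

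Other cases, SE 1.971:

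| True effect | Dropout | Significant results with no tip by 100% |
|---|---|---|
| 7 | 10% | 95% |
| 7 | 30% | 70% |
| 6 | 20% | 76% |
| 5 | 20% | 64% |
| 4 | 20% | 53% |
| 3 | 20% | 42% |
| 5 | 30% | 41% |

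A 400-run simulation at δ = 7 and 20% dropout (imputation by arm; assumed AR(1) correlation 0.7 and placebo change −9; Visit 7 analysed by difference in means, not the full MMRM) gave 87% with no tip and a median tipping point of 190%.

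**Mean-change scale.** A 100% penalty is now the whole AR19 mean change, which depends on the placebo change. The documents do not give that, so two values are assumed.

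- Placebo −9, AR19 −16: estimate at 100% = 7 − 0.2 × 16 = 3.8, z = 3.8/1.971 = 1.93. The result tips inside the range, at 12.9/16 = 81%.
- Placebo −5, AR19 −12: estimate = 7 − 0.2 × 12 = 4.6, z = 2.33. It has not tipped; 12.9/12 = 108%.

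In simulation 39% and 59% of significant results, respectively, end without a tip.

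**Comparison with sensitivity analysis one.** Copy Reference imputes from the placebo model given the subject's observed scores, so an AR19 dropout keeps part of any benefit already seen. A 100% penalty subtracts the full Visit 7 difference from the MAR imputation. In the simulation the mean estimate was 6.50 under Copy Reference and 6.00 at the 100% penalty. The significance verdict agreed in 92% of runs (95% at correlation 0.4).

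**The case against.** Four points can be made for the SAP.

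1. **The end point is not fixed at placebo.** Step 3 and the shift values support a mean-change scale, which goes past placebo whenever placebo subjects improve. This stands. A reader might infer from Step 5 alone that outcomes worse than placebo are never examined; the documents support that only on the treatment-difference reading.
2. **The analysis is not a copy of sensitivity analysis one.** A reader might infer duplication because both refer to placebo-like outcomes. The imputation models differ, the estimates differ, and the tipping-point analysis also reports the difference, interval and p-value at every 5% step. What remains is that, on the treatment-difference scale, it ends at nearly the same assumption and goes little further.
3. **A bounded search is legitimate.** Worse outcomes in the SAP means worse than the primary assumption, not worse than placebo. Remaining significant with every AR19 dropout at placebo level is a valid finding. The range also catches the most fragile results: with SE 2.018, observed differences from 4.52 to 5.65 tip inside it. This stands, but the bounded statement still leaves the distance to the tipping point unknown.
4. **The analysis is supportive and conditional.** The SAP says the sensitivity analyses may be performed, and drops them if dropout is below 2%. This limits the severity.

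**Conclusion.** The point holds in two parts. The conflict over the penalty scale is plain in the text and needs no assumptions. The early stop follows on the treatment-difference scale: at the planned effect and dropout, about 84% to 86% of significant results would end with no tipping point, which would lie near 12 to 13 points.

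That share is not general. It is about 42% at a true effect of 3 with 20% dropout and 41% at 5 with 30%. On the mean-change scale it is about 39% with an assumed placebo change of −9, so most results tip inside the range, and 59% with −5, so most do not.

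The figures assume equal dropout across arms and a difference-in-means approximation to the MMRM. The simulated ones also assume a visit correlation, a placebo change and a timing of dropout, none of which the documents give. The primary test and its decision rule are not affected. This is a cheap improvement to a supportive analysis.

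**What to change.** In SAP section 7.1.1.2:

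- Define the penalty once, as AISRS points added to the imputed AR19 Visit 7 values, separately for each dose.
- Rewrite the shift values, the stated worst case and Steps 1, 3 and 5 to match. Deleting the 100% clause from Step 5 alone would leave the introductory text and the steps in conflict. Step 1 should also name Visit 7 (Week 5), since it now refers to Week 7.
- Replace the 100% stop with continuation past a placebo-like response until the 97.5% confidence interval includes zero or the imputed scores reach the AISRS limit (range 0 to 54). State how an imputed score pushed above 54 is handled.
- For each dose, report the tipping penalty in points and the implied mean change of AR19 dropouts, beside the placebo and AR19 completer means.

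At the planned inputs this means running to about 200% of the treatment difference, and to about 400% if dropout is 10%. The cost is SAP wording and more runs of the same program. Some large penalties may be judged implausible: at 10% dropout the tip is 3.69 × 7, about 26 points, nearly half the scale. The completer means beside it let a reader make that judgement.

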7.1.2 Assessment Time Windows

Data will be summarized based on the recorded visit; no visit windowing will be conducted. Visit 7 must be performed as scheduled based on the protocol, allowing for consistent and reliable efficacy measurements.

7.2 Efficacy Measurements

7.2.1 Adult ADHD Investigator Rating Scale (AISRS)

The AISRS is a validated 18-item scale that corresponds directly to the 18 ADHD items in the Diagnostic and Statistical Manual of Mental Disorders. It includes adult prompts for each item. The AISRS will be used to determine trial eligibility. An AISRS assessment will be completed at Study Visits 1 through 7. The Investigator or other designated, qualified individual from the study research team will complete the assessment.

Each item is scored from a range of zero (reflecting no symptoms) to 3 (reflecting severe symptoms) with total scores ranging from zero to 54. Higher AISRS total scores signify greater severity of ADHD symptoms.

The following AISRS scores will be assessed:

- AISRS Hyperactivity/Impulsivity subscale score (sum of even numbered items 2 through 18)
- AISRS Inattentiveness subscale score (sum of odd numbered items 1 through 17)
- AISRS total score (sum of all items)

See Appendix 14.2 for more details on these items. Missing or invalid data for individual questions will be handled by rules described in Section 7.1.1.1.

7.2.2 Clinical Global Impression Scale (CGI)

The Clinical Global Impression Scales are used to measure features associated with ADHD. A global assessment of disease severity (CGI-S) will be completed at Study Visits 1 through 7. A global assessment of disease improvement (CGI-I) relative to baseline will be completed at Study Visits 3 through 7. The Investigator or designated, qualified individual from the study site will perform the assessment. The severity of a subject's ADHD symptoms will be rated on a 7-point scale ranging from 1 (normal) to 7 (among the most extremely ill subjects).

The subject's current disease status will be classified as follows:

1 = Normal, not at all ill.

2 = Borderline ill.

3 = Mildly ill.

4 = Moderately ill.

5 = Markedly ill.

6 = Severely ill.

7 = Among the most extremely ill subjects.

The subject's disease improvement relative to Baseline (Visit 2) will be classified as follows:

1 = Very much improved.

2 = Much improved.

3 = Minimally improved.

4 = No change.

5 = Minimally worse.

6 = Much worse.

7 = Very much worse.

7.2.3 Mini International Neuropsychiatric Interview 7.0.2 (MINI)

The MINI is a short, structured diagnostic interview developed for DSM-5™. It assesses the 15 most common psychiatric diagnoses and can be completed in about 15 minutes. The MINI will be completed at Screening.

7.2.4 Conners' Adult ADHD Diagnostic Interview for DSM-IV™ (CAADID)

The CAADID is a structured interview that assesses childhood and adult ADHD symptoms. Although the version used was designed for DSM-IV™, it can be adapted to make an ADHD diagnosis using DSM-5™ criteria. The CAADID will be completed at Screening.

